6.10.13 Limitations and Planned Solutions

This study has limitations. First, we require the enrollment of at least 50 HCA hospitals. While we believe this is possible due to our previous trial of 43 HCA hospitals, should enrollment drop unexpectedly to less than 50, we will pursue an elongation of the 18-month trial, (NOTE: intervention was extended to a 21-month trial in June 2015). Secondly, if hospital committee approvals for trial protocols are delayed, we will expand the phase-in period to a total of 3 months. We note that our prior trial completed phase-in within 30 days. Third, if decolonization is significantly better at preventing infection, we appreciate that we are unlikely to be able to distinguish between effects of chlorhexidine and the effects of active encouragement to bathe or shower. Nevertheless, the results of this study would reflect a real world intervention which would likely entail both processes.

Cluster randomization does not allow every question of interest to be addressed. It typically results in more misclassification of exposure than individual randomized controlled trials do, either because individual providers choose to use a non-recommended regimen for some patients, or they fail to adhere fully to the assigned regimen. To the extent that the frequency of failure is consistent with the level that occurs in usual clinical practice, these failures are part of the overall effectiveness measure. Thus, cluster randomization in inpatient systems may offer a relatively low-cost and broadly generalizable means to examine many of the priority topics for comparative effectiveness research. In addition, this study design does not allow for blinded assignment or implementation. Nevertheless, this reflects the pragmatic nature of our intervention and directly mirrors the design and implementation of hospital quality improvement initiatives.

6.10.14 Dissemination Plan

We will disseminate trial results through presentations at national meetings, and publication in peer-reviewed journals, and press releases. We will also use our contacts at the CDC, membership on the national advisory committee that recommends infection prevention strategies (HICPAC – the Healthcare Infection Control Practices Advisory Committee), membership on the Institute of Medicine Roundtable on Value & Science-Driven Health’s Innovation Collaborative on Clinical Effectiveness, participation in national societies such as the Infectious Diseases Society of America (IDSA) and the Society for Healthcare Epidemiology of America (SHEA), and contacts with state departments of public health to disseminate trial results.

Through the Collaboratory’s website and dissemination mechanisms, we will also make our decolonization toolkit publicly available. This toolkit includes information about healthcare-associated infections, mupirocin protocols, chlorhexidine bathing protocols (for showering and bed bathing), extensive product compatibility guidance, frequently asked questions guides, wall charts for patient bathing instruction, audio podcasts and special coaching calls.

6.20 Aim 2: Assess whether universal chlorhexidine bathing and selective MRSA decolonization result in increased resistance to chlorhexidine or mupirocin among bacterial strains collected during the trial.

In order to assess whether routine use of chlorhexidine for bathing and selective use of mupirocin for MRSA decolonization engenders increased resistance to these agents over the course of the trial, we will collect bacterial strains from participating units during the baseline and intervention periods in each study arm.

6.20.1 Preliminary Data (Confidential, do not cite or distribute)

We collected 4,321 MRSA isolates during the REDUCE MRSA trial, a trial of decolonization with chlorhexidine and mupirocin in ICUs to reduce MRSA carriage and infection. 993 strains in the baseline period and 3,328 in the 18-month intervention period were collected from microbiology laboratories in 43 HCA hospitals across 3 arms. Strains were assessed for the presence of chlorhexidine resistance and high-level mupirocin resistance, which has been associated with decolonization failure.^{55 68 217}

Chlorhexidine resistance was essentially non-existent: there was a single chlorhexidine resistant isolate which occurred in the usual care arm during the intervention period. No formal analyses were pursued.

At baseline, high-level mupirocin resistance was present at 6.7% (67/993). There were no significantly different increases across the arms between baseline and intervention periods. In the targeted decolonization arm of the REDUCE MRSA Trial, which most resembles the proposed intervention in the ABATE Infection Trial, high-level mupirocin resistance was 5.9% in the baseline period and 5.4% in the intervention period.

Processes and materials used in the collection of bacterial isolates during the REDUCE MRSA trial will be replicated by trial investigators for the ABATE Infection Trial as described below.

6.20.2 Strain Collection

Strain collection will include MRSA and other pathogens since chlorhexidine targets a broad range of microbes and rare cases of resistance have been reported in select gram-negative bacteria, namely acinetobacter, burkholderia, E coli, klebsiella, proteus, pseudomonas, serratia, and stentrophomonas.^{218 219 220} Study staff will coordinate with each clinical microbiology laboratory director for the collection of MRSA and these gram negative bacteria for a 9-month period toward the end of both the baseline and intervention periods for each arm. A total of 2,400 MRSA and 2,800 gram negative bacteria will be collected.

Trial staff will provide each microbiology laboratory with a toolkit with detailed instructions about strain collection, including the list of pathogens, participating units, and time window for collection. Microbiology technologists will be instructed to target strains with a collection date at least 2 days after admission based upon unit location and admission date, which are available during usual specimen processing. Similar to our prior trial, the toolkit will include a Step-by-Step instruction guide, a Frequently Asked Questions (FAQ) sheet, FedEx mailing instruction sheet, deidentified study ID labels, collection log sheets with clipboard, shipment packing list, and shipping schedule (see example from prior trial, **Appendix E, G**). In addition, a quick reference wall cling will be sent that provides a streamlined diagram of the key elements for collection (see example from prior trial, **Appendix F**). Details will be reviewed in laboratory-specific coaching calls.

Chocolate agar slants and shipping kits (STP-250MD, Saf-T-Pak Inc.) will be sent to each laboratory on a regular basis for monthly batch shipment of strains. Initially, trial staff will contact laboratory liaisons once weekly until processes are in place. Trial staff will contact each laboratory prior to each anticipated shipment.

Trial staff will receive faxed log sheets that include the hospital, unit, collection date, specimen source, and coded ID. A separate fully-identified log sheet will be sent internally to HCA co-investigators who will use identifiers to subsequently link coded specimen study IDs to coded individual-level trial data during the analysis phase. In the event that resistance is found to be engendered by decolonization, this linkage will allow further exploration regarding patient exposure to study products prior to specimen collection.

6.20.3 Strain Processing

For the collection of MRSA and gram negative bacterial isolates (performed by HCA staff) at participating HCA hospitals from their microbiology laboratories, log sheets that identify the patients from whom the isolates arise will be provided to HCA corporate study investigators and retained for the duration of the study period. Direct patient identifiers will not be shared external to HCA. All information transferred to Rush University, the isolate collection core and the research analytic core at the Department of Population Medicine (DPM) at Harvard Pilgrim Health Care, will be stripped of direct identifiers and replaced by a coded identifier. Isolates will be shipped to [name] in the Division of Clinical Microbiology, our Co-Investigator at the

Rush University Medical Center in Chicago, IL. Bacterial identification will be confirmed by standard microbiologic methods. For MRSA isolates, resistance to methicillin will be verified by ceftioxin disk testing²²¹ and mupirocin susceptibility will be assessed by the E-test method (bioMérieux, Durham, NC). Mupirocin resistance will be determined according to Eltringham.²²²

All bacterial isolates will have susceptibility to chlorhexidine determined by a microtiter method using 20% aqueous chlorhexidine digluconate (Sigma-Aldrich LLC, St. Louis, MO) diluted in broth medium appropriate for the microbe tested.²¹⁸ Since national standards do not yet exist for chlorhexidine resistance, we will define resistance as a minimum inhibitory concentration (MIC) of chlorhexidine that is outside of the reported wildtype distribution for each microbial species. Based upon recent literature, we will use a resistance breakpoint of ≥ 8 mcg/ml for MRSA,¹⁷ ≥ 32 mcg/ml for klebsiella, pseudomonas, and serratia,²¹⁶⁻²¹⁷ and ≥ 64 mcg/ml for burkholderia, proteus, and stenotrophomonas.²¹⁵⁻²¹⁷ These species were chosen because of their relatively high chlorhexidine MICs compared to other bacterial species and/or their association with outbreaks linked to contaminated commercial chlorhexidine products (burkholderia). In addition to assessing MIC breakpoints, we will evaluate the proportion of strains with a high MIC within the susceptible range between baseline and intervention strains. Decreased susceptibility to chlorhexidine has been associated with the presence of various multidrug efflux pumps.^{223 224 225} If chlorhexidine resistant (or nearly resistant) isolates are identified, we will use polymerase chain reaction methods to evaluate isolates for the presence of efflux pump genes. If efflux pump genes are found, additional characterization of resistance may be done including assays to quantify expression of efflux pumps and to measure the effect of inhibition of efflux on chlorhexidine MICs.

6.20.4 Analysis

For mupirocin and chlorhexidine separately, we will report the proportion of resistant isolates in each arm in the baseline and intervention periods. We will test differences between arms in resistance by fitting a generalized linear mixed logistic regression model with arm, baseline vs. intervention period, and their interaction as predictors. The interaction term assesses whether the difference in the probability of resistance between the baseline and intervention periods is significantly different between arms.

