6.20.5 Power and Sample Size

Based upon our recent trial data, we assume high level mupirocin resistance in 0.07 of MRSA isolates at baseline. We estimate collection of 2,400 isolates (600 per arm in the each of the intervention and baseline periods). As in UH3 Aim 1, power is based on a post-only comparison of 1200 subjects, 24 per hospital. Assuming intracluster correlation of 0.001, we will have 80% power to detect 0.12 high level mupirocin resistance in the decolonization arm, assuming that resistance remains at 0.07 in the usual care arm.

For both MRSA and gram negative bacteria, we will calculate the proportion of isolates resistant to chlorhexidine. If the proportion of MRSA that is resistant is truly as large as 0.1%, we will have at least a 90% probability of detecting ≥ 1 resistant strain among 2400 isolates, 70% among the 1200 post-period isolates, and 45% among 600 isolates in the post period in the intervention arm. If the resistance rate increases to 0.5%, we have a 95% chance of observing at least one case in the 600 intervention isolates from the follow-up period.

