### 2.2 Statistical Analysis

All outcomes will be assessed similarly. Here, we use the example of the primary outcome: clinical cultures with MRSA or VRE (first per patient). MRSA and VRE clinical cultures will be attributed to participating units if the collection date occurred >2 days after admission to that unit through two days after discharge from that unit. This attribution is consistent with CDC guidance for surveillance of nosocomial infections.

Main trial results will be based upon as-randomized, unadjusted analyses using proportional hazards models to account for patients' variable tenure in the unit. This is necessary for the usual reasons: dichotomizing patients into those with vs. without infections would require us to define a fixed time-frame (within first x days of eligibility, ignoring some infections and omitting patients with shorter stays) or to ignore exposed time (counting infection during unit stay regardless of different length of stay). In addition, power is greater for proportional hazards models than for logistic regression models.

Clustering within hospital will be accounted for using shared frailties. The frailties are added model terms that allow unique hazards ratios for each hospital, and are necessary to account for clustered randomization. Model terms will include individual-level data on arm, hospital, outcome events, trial period (baseline vs. intervention) and an interaction term between trial period and arm. The assessment of trial success will be determined by the significance of the interaction term, which assesses whether the difference in hazard between the baseline and intervention period differs significantly between the two arms. We can write a simple version of the model symbolically as:

$$\lambda_{ij}(t) = \lambda_0(t)e^{\beta_1 Arm_{ij} + \beta_2 Period_{ij} + \beta_3 Arm_{ij} * Period_{ij} + \gamma_i}$$

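### Aim 2 analyses isolates with no limit per patient and no stated within-patient term, so its resistance test and its 80% power are sound only if the isolates come from different patients.

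*Protocol*

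**What the plan says.** - **Selection (Protocol 6.20.2).** Laboratories are told to "target strains with a collection date at least 2 days after admission", for MRSA and listed gram-negative species from participating units within a collection window. No rule says how many isolates one patient may contribute. A link to patients is planned: the health system's investigators will "link coded specimen study IDs to coded individual-level trial data during the analysis phase".
- **Analysis (Protocol 6.20.4).** The summary is by isolate: "we will report the proportion of resistant isolates in each arm in the baseline and intervention periods". The test is made by "fitting a generalized linear mixed logistic regression model with arm, baseline vs. intervention period, and their interaction as predictors". The random effects are not named, and no patient-level term is mentioned. "The interaction term assesses whether the difference in the probability of resistance between the baseline and intervention periods is significantly different between arms".
- **Power (Protocol 6.20.5).** "we assume high level mupirocin resistance in 0.07 of MRSA isolates at baseline". The section expects 600 isolates per arm in each period, and "power is based on a post-only comparison of 1200 subjects, 24 per hospital". With an intracluster correlation of 0.001 it claims 80% power for 0.12 against 0.07. The same section gives probabilities of seeing at least one chlorhexidine-resistant MRSA isolate.
- **Contrast (Protocol 6.10.11 and SAP 2.2).** The primary outcome is defined as "clinical cultures with MRSA or VRE (first per patient"). The SAP lists emergence of resistance in Table 1 but adds no rule on isolates.

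**The concern.** Two isolates from one carrier in the same period will often be the same strain, so the second adds little information about how common resistance is. Counted as separate units, such pairs overstate the effective sample size. They also give more weight to patients who stay culture-positive. If the model has no term that picks up the dependence, its standard errors are too small. Whatever the model, the information available is closer to the number of patients than to the number of isolates, so power is below the stated value.

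This matters because Protocol 4.1 (Element 4) names resistance to the two agents as the potential harm that the trial will evaluate. An apparent difference between arms could be spurious, and a real one could be missed more often than the plan says.

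**Working it through.** **1. The plan's own figure.** Inputs from 6.20.5: p1 = 0.07, p2 = 0.12, 600 isolates per arm in the intervention period, 24 per hospital, hospital correlation 0.001. A two-sided alpha of 0.05 is assumed, since it is stated only for the Aim 1 model.

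- Hospital design effect: 1 + 23 × 0.001 = 1.023, so n = 600/1.023 = 586.5 per arm.
- Continuity-corrected power: Φ{[0.05 − 1/n − 1.96·√(2·0.095·0.905/n)] / √[(0.07·0.93 + 0.12·0.88)/n]} = Φ{(0.0483 − 0.0336)/0.01706} = 80.6%. Without the correction it is 83.2%.

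The 80% therefore reproduces when each isolate is one unit and only hospital clustering is allowed for.

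**2. Adding repeats.** Let m be isolates per patient and ρ the within-patient correlation of resistance. The extra design effect is DE = 1 + (E[m²]/E[m] − 1)·ρ. If a share f of patients gives two isolates and the rest one, E[m] = 1 + f and E[m²] = 1 + 3f. With ρ = 1 and f = 0.10, DE = 1.3/1.1 = 1.182. The values of f and ρ are assumptions, taken as equal in all four arm-by-period cells, so the interaction's standard error is understated by √DE. If the dependence is ignored, the type I error is 2·[1 − Φ(1.96/√DE)].

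| Patients giving two | DE | √DE | Effective n per arm | Two-sided type I error if ignored | Post-only power, corrected (uncorrected) | Distinct patients per arm | Corrected power, first isolates only |
|---|---|---|---|---|---|---|---|
| 0% | 1.000 | 1.000 | 587 | 5.0% | 80.6% (83.2%) | 600 | 80.6% |
| 10% | 1.182 | 1.087 | 496 | 7.1% | 73.2% (76.7%) | 545 | 76.5% |
| 20% | 1.333 | 1.155 | 440 | 9.0% | 67.6% (71.6%) | 500 | 72.5% |
| 50% | 1.667 | 1.291 | 352 | 12.9% | 56.9% (61.9%) | 400 | 61.9% |

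With ρ = 0.8 the corrected power in the last three rows is 74.7%, 70.0% and 60.9%, and the type I error is 6.7%, 8.2% and 11.3%.

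**3. Dependence on the random effects.** A simulation used 25 hospitals per arm and 24 isolates per hospital and period. An interaction test that ignored patients rejected a true null 9.4% of the time with 20% of patients giving two isolates, and 12.3% with 50%. A test on each hospital's change between periods stayed at about 5%, but its power fell from 60% with no repeats to 48% and 39%. Repeats fall within a hospital and period, so a hospital-by-period term would largely protect the error rate. It would not restore the lost information.

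**4. Detection probabilities in 6.20.5.** These are 1 − (1 − p)^n with every isolate counted separately:

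- p = 0.001: 90.9% (n = 2,400), 69.9% (1,200) and 45.1% (600).
- p = 0.005: 95.1% (600).

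They match the stated 90%, 70%, 45% and 95%. With 10% to 50% of patients giving two concordant isolates, 2,400 isolates are 2,400/1.1 = 2,182 to 2,400/1.5 = 1,600 patients. The first figure becomes 1 − 0.999^2182 = 89% to 1 − 0.999^1600 = 80%. For 600 isolates (545 to 400 patients) the 45% becomes 42% to 33%.

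**The case against.** The case against has real force on several points.

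- **Benign reading.** The word subjects in 6.20.5 can mean 1,200 patients with one isolate each. Protocol 6.10.11 and SAP 2.2 say outcomes are handled alike before giving the first-per-patient example, and emergence of resistance is a listed outcome. This leaves the text ambiguous. It does not settle the matter, because Aim 2 has its own non-survival model and reports proportions of isolates.
- **Laboratory toolkit.** A repeat rule could sit in the collection instructions, which are not part of these documents. That is possible, but the analysis section should still state its unit.
- **Recoverable shortfall.** Section 6.20.6 allows a longer collection window. This helps only if progress is counted in patients.
- **Cost of a first-isolate rule.** Used alone, it could discard later isolates taken after more exposure, where resistance would emerge. This stands, and the fix allows for it.

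Four stronger readings are tempting and are not supported:

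- **That isolates are treated as wholly independent.** The model is mixed, and the mupirocin power includes a hospital correlation.
- **That the model will understate the standard error.** That requires repeats to enter and the random effects to leave their correlation unmodelled.
- **That a false signal of harm necessarily exceeds 5%.** The 7.1% to 12.9% is two-sided. Half of it, about 3.6% to 6.5%, lies in the harmful direction, against a nominal 2.5%.
- **That the chlorhexidine test is inflated in the same way.** The calculations are for mupirocin. At the chlorhexidine rates considered in 6.20.5, 600 isolates would yield 0.6 to 3 resistant ones.

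**Conclusion.** The concern holds conditionally. Followed literally, Aim 2 lets concordant repeats from one patient count as separate units, in the test and in the power statement. If 10% to 50% of patients give two fully concordant isolates, the 80% post-only power becomes roughly 73% to 57% (continuity-corrected). With only a hospital intercept, the two-sided mupirocin interaction test would run at about 7% to 13%. The documents give neither a repeat rate nor a within-patient correlation, so these sizes rest on assumption. If the 600 isolates per arm are from 600 different patients, the 80% is correct as stated.

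The point deserves a change because the analysis as written would be worse if repeats occur, and the patient link needed to prevent this is already planned. A separate matter, not counted here, is that the power is for a post-only comparison while the planned test is the arm-by-period interaction.

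**What to change.** **Section 6.20.4.** Define the main analysis as the first eligible isolate per patient, species and period, identified through the specimen-to-patient link in 6.20.2. Name the random effects: hospital and hospital-by-period. Keep all isolates in a secondary analysis with a patient-level random effect or patient-clustered variance, so that resistance emerging after exposure is not lost.

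**Section 6.20.5.** State that the 600 per cell and the detection probabilities refer to distinct patients, or restate both for the expected number of distinct patients. If 600 patients per cell is the target, the monitoring in 6.20.6 should count patients.

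**Cost.** A few sentences and one de-duplication step; laboratories can go on sending every isolate. The stated sample size may be smaller and the stated power somewhat lower. With 10% of patients giving two isolates, 600/1.1 = 545 patients per arm remain, and the corrected post-only power is 76.5%.

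### For chlorhexidine resistance in MRSA, the planned arm-by-period logistic interaction is the wrong formal test at near-zero rates: resistance confined to the decolonization arm after baseline gives a p-value near 1

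*Protocol*

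**What the plan says.** Protocol 6.20.4 is the only place that specifies the resistance analysis. SAP 2.1 lists emergence of resistance among the outcomes for secondary manuscripts, and SAP 2.2 adds no method specific to it. For mupirocin and chlorhexidine in turn, 6.20.4 first promises a description: "we will report the proportion of resistant isolates in each arm in the baseline and intervention periods". It then gives the test: "We will test differences between arms in resistance by fitting a generalized linear mixed logistic regression model". The predictors are arm, period and the product of the two. The interaction carries the inference. No exact, penalized or other sparse-data method is named.

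The expected counts come from two places. Section 6.20.1 says of the prior trial: "Chlorhexidine resistance was essentially non-existent: there was a single chlorhexidine resistant isolate". That is one among 4,321 MRSA isolates, and the section adds that no formal analysis was done. Section 6.20.5 plans 2,400 MRSA isolates, "600 per arm in the each of the intervention and baseline periods". Its chlorhexidine example begins "If the proportion of MRSA that is resistant is truly as large as 0.1" per cent and goes on to 0.5%. For these rates it gives only the chance of seeing at least one resistant isolate. The one comparative power figure in Aim 2 is for mupirocin, and it rests on the intervention period alone, not on the interaction.

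Section 6.20.3 adds a second chlorhexidine readout: "we will evaluate the proportion of strains with a high MIC within the susceptible range between baseline and intervention strains".

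**The concern.** An interaction on the logit scale needs events in the reference cells to define the odds ratios being compared. Where chlorhexidine resistance is almost absent, those cells will usually be empty. The pattern of most interest, resistance appearing only in decolonized hospitals after the intervention starts, is then the one that the test cannot recognise.

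Aim 2 exists to answer whether decolonization engenders resistance, and section 4.1 lists this among the potential harms to be compared between arms. A p-value near 1 printed beside 12 versus 0 resistant isolates would point readers the wrong way, on a strategy that the protocol expects to become practice for 40 million patients a year.

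**Working it through.** **Inputs.** 600 MRSA isolates per arm and period, and rates of 0.1% and 0.5% (6.20.5). Prior-trial rate 1/4,321 = 0.023% (6.20.1). Assumptions: two-sided 5% level (not stated for Aim 2; borrowed from 6.10.11), and independent isolates with no hospital effects. Rates of 1% and above are illustrations and are not in the protocol.

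**1. The protocol's own figures.** P(at least one) = 1 − (1 − p)^n.
- 0.1%: n = 2,400 gives 90.9%, n = 1,200 gives 69.9%, n = 600 gives 45.1%.
- 0.5%: n = 600 gives 95.1%.

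The protocol states at least 90%, 70%, 45% and 95%, so all four reproduce. They are chances of observing an isolate, not power to compare arms.

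**2. Empty cells.** With three reference cells at 0.1%, the chance that all contain an event is (1 − 0.999^600)^3 = 0.451^3 = 0.092. At least one is empty in about 91% of trials. At about 0.03% (one resistant isolate among the prior trial's 3,328 from its intervention period) the figure is about 99%.

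**3. What the test does with particular tables.** Order: control baseline, control intervention period, decolonization baseline, decolonization intervention period; 600 per cell.

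| Counts | Interaction, likelihood ratio | Fisher, intervention period |
|---|---|---|
| 0/0/0/12 | p = 1.0 | p = 0.0005 |
| 0/0/0/60 | p = 1.0 | p about 4 × 10⁻¹⁹ |
| 1/0/0/12 | p = 0.008 | p = 0.0005 |
| 1/1/1/12 | p = 0.16 (Wald 0.15) | p = 0.003 |

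The first two rows follow from the algebra. Set the arm and period effects both to M and the intercept to −2M + c. As M grows, the first three fitted probabilities go to zero and the fourth stays at the value set by c. Main effects alone then fit perfectly and nothing is left for the interaction, however large the last count. The Wald statistic is not estimable in these tables. Between rows one and three, a single isolate in the control arm at baseline moves p from 1.0 to 0.008.

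**4. Power, reference cells at 0.1%.** Ranges show separate simulation runs of 1,500 to 3,000 trials.

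| Rate in decolonization arm, intervention period | Wald, empty cell counted non-significant | Wald, 0.5 added to each cell | Likelihood ratio | Fisher, intervention period |
|---|---|---|---|---|
| 0.5% | 0% | 0.6% | 10% | 5–6% |
| 1% | 0.1% | 3% | 19–22% | 39–41% |
| 2% | about 1% | 14% | 30–33% | 92–93% |
| 3% | about 2% | 27–30% | 35–40% | over 99% |

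**5. Why 0.5% is out of reach.** Fisher's test at 600 per arm needs 6 versus 0 (p = 0.031); 5 versus 0 gives p = 0.062. At 0.5% the expected count is 600 × 0.005 = 3. Even 0 of 600 has an exact 95% upper limit of 1 − 0.025^(1/600) = 0.61%, so it does not exclude 0.5%.

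**The case against.** Several counter-arguments have force.

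- *The signal would be visible.* A reader might infer that real emergence would be reported only as no significant difference. The documents do not support that. Section 6.20.4 commits to proportions by arm and period, 6.20.3 adds high-MIC proportions and efflux-pump testing of resistant or nearly resistant isolates, and 6.20.2 provides linkage to patient exposure. This stands. But none of these is a valid comparison of arms, and the only prespecified inference is the one that fails.
- *The power need not be 1–2%.* Those figures belong to a Wald test with every empty-cell table scored as a failure. Section 6.20.4 does not specify Wald, and a likelihood-ratio test reaches roughly a third at 2% and above. This stands too, but it is still far below the intervention-period comparison and turns on where a stray isolate falls.
- *An exact test does not rescue the protocol's own contrast.* At 0.1% versus 0.5% it does no better than the likelihood-ratio interaction. The limit there is the number of events. The choice of test matters from about 1% upward.
- *Clustering.* The Fisher figures ignore hospital clustering. Twelve isolates from one hospital would be much weaker evidence than the p-value suggests, so an ordinary Fisher test is not the right replacement.
- *High-MIC wording.* Read alone, the 6.20.3 sentence describes a before–after comparison. Section 6.10.7 makes the purpose differential between arms, so this is probably loose drafting.
- *Gram-negatives.* It is tempting to extend the point to the other organisms collected, "namely acinetobacter, burkholderia, E coli, klebsiella, proteus, pseudomonas, serratia, and stentrophomonas". The protocol calls their resistance rare but gives no rate, so the size is unknown. E. coli and acinetobacter have no numeric breakpoint, but 6.20.3 has a general definition (MIC outside the species' wild-type distribution). That is missing detail, not undefined resistance.

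**Conclusion.** The point holds for chlorhexidine resistance in MRSA. At the rates the protocol cites, the prespecified interaction usually meets an empty cell and returns p near 1 for resistance confined to the decolonization arm after baseline, whatever its extent. At 2% against 0.1% its power is about 1% to 33%, depending on the form of the test, against about 92% for an intervention-period exact comparison. At 0.5% none of the tests examined exceeds about 10%.

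The figures assume 600 isolates in every cell, a 5% two-sided level and independent isolates. Clustering would reduce the 92%; by how much cannot be said, because the documents give no intracluster correlation for chlorhexidine resistance. The p-value of about 1 for the 0/0/0/k tables rests on algebra and needs no assumed rate.

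This is a secondary outcome whose raw proportions will be shown, so the change should be made but does not threaten the trial's main result.

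**What to change.** In Protocol 6.20.4, keep the interaction model for mupirocin and treat chlorhexidine separately:

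1. Report counts of resistant isolates by arm and period, and by hospital.
2. Compare arms in the intervention period with a hospital-level permutation test that respects the randomization strata, or an exact test that allows for clustering, with a confidence interval for the difference.
3. State in advance that a non-significant result does not exclude emergence at rates such as 0.5%.
4. In 6.20.3, word the high-MIC comparison as arm-by-period.

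An arm-by-period analysis of log2 MIC by species, with a hospital effect, could be added as support. It is optional: its power depends on an MIC standard deviation and an intracluster correlation that the documents do not give, and a small shift may not matter clinically.

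The cost is wording and modest extra analysis, with no new isolates or assays. The intervention-period comparison gives up the baseline data, which matters little when baseline counts are near zero, and 6.20.5 already bases its mupirocin power on that period alone.
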